#### **Design and Outcomes**

The study will use a randomized multi-site (Portland, Albuquerque, Madison) clinical trial assessing feasibility and across-site equivalence of all study procedures. Three study arms include MBRT, an attention control (SME), and a no-intervention control (NIC). Outcomes include physiological, behavioral, and psychological indices of officer wellbeing, resilience, and excessive use of force in law enforcement officers.

Participants will complete baseline, post-intervention, and 3- and 6-month follow-up assessments. Assessments include self-report measures, a computerized attention task, and a self-administered dried blood spot test. Participants will be invited to participate in a post-intervention telephone feedback interview. Twelve-month departmental excessive use of force data will be collected from police department databases, and will involve neither direct participant interaction nor compensation.

## Interventions and Duration

Participants in all 3 arms will be involved in the study for baseline data collection, collected within the 14 days prior to the intervention period, followed by an 8-week intervention period

during which participants randomized to MBRT or SME will receive an active intervention. Participants in the NIC condition will not receive any intervention. There will then be a 6-month follow-up period ( $\pm$  7 days), totaling 7.75 - 8.25 months total of study involvement. Although 12-month data are collected via police department (e.g., BlueTeam) databases, participant involvement ends after the 6-month follow-up assessment point.

## **Sample Size and Population**

We will recruit 104 law enforcement officers (52 at Albuquerque, 26 at Portland, and 26 at Madison). Using a 2:1.5:1 randomization allocation ratio for MBRT, SME, and NIC conditions, respectively, across three sites, 47 participants will be randomized to MBRT; 35 to SME; and 22 to NIC. Participants will be stratified by gender to ensure equivalent gender representation across conditions.

All participants will be invited to participate in individual feedback interviews via phone after the post-course assessment.

## **1. STUDY OBJECTIVES**

### **1.1 Primary Objective**

#### **Objective 1: Enhance efficiency of recruitment, engagement, and retention across sites.**

We will successfully enroll 52 LEOs at Albuquerque, 26 at Portland, and 26 at Madison, with an *across-site average* of 20% female and 35% racial/ethnic minority participants; 85% of participants will attend  $\geq$  6 MBRT or SME sessions (i.e., treatment completer), and complete 75% of assigned homework. Based on 80% retention at *3 months* in the recent R21, enhanced retention efforts will result in  $\geq$  80% at *6 months*.

Per NCCIH SARP guidelines, we will gauge accrual and retention by accrual of  $\geq$  80% but no higher than 150% of benchmark number at a given time point, study initiation delay of  $\leq$  1 accrual reporting period ( $\sim$ 4 months), and actual loss to follow-up rate  $\leq$  20%.

**Objective 2: Ensure fidelity and equivalence of lab, assessment, and data management procedures across sites.** 100% of staff will complete trainings in research ethics, an NIH Good Lab Practice course, and all assessment and lab procedures. Throughout the study, there will be  $\leq$  5% rate data procedural errors, tracked in REDCap (same procedure used in R21 study). Based on the R21 study, we expect  $\leq$  15% missing data due to omitted or refused completion of measures from active participants. Collection of self-report measures will be acceptable to LEOs at all sites, i.e., all assessments will be completed in the allotted time, assessment burden will be acceptable, and questionnaire items will be relevant and acceptable ( $\geq$  75% of LEOs rate assessment protocol as “reasonable” or “very reasonable” in content, clarity and time burden). We will obtain departmental excessive use of force (i.e., BlueTeam or other departmental data) for 100% of participants at all sites in designated period (1 month to assemble pre-baseline, and 1 month to assemble at 12-month follow-up). Biweekly reviews will yield 100% adherence to data management protocol at both data collection sites.

**Objective 3: Optimize intervention training procedures and ensure fidelity to intervention protocols across sites.** All study MBRT and SME interventionists will complete intensive clinical trainings, demonstrate 90% fidelity on Adherence and Competence scales, and

subsequently maintain  $\geq 85\%$  overall fidelity (including session content coverage, presence of main themes, and global skills). Interrater reliability between all coders will be  $\geq .75$ , which is an established criterion for excellent reliability.

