Intervention locations at both study sites were carefully chosen, in collaboration with the corresponding police departments, to ensure low threshold accessibility. Per police department-recommended criteria, locations are central, accessible via public transportation, have parking options, and do not have signage that indicates mental health or addiction services, which can be a barrier for law enforcement participation. Space allows for compliance with social distancing recommendations.

Enrollment for the study will take place during Year Two of the grant from Month 2 through Month 8. The first phase of baseline data collection will occur during Month 4 of Year 2, directly preceding the beginning of MBRT and SME training for the first cohort of participants in Months 4 and 5. The second phase of baseline data collection is delayed due to COVID-19 restrictions. It will now occur during Year Three in Month 1, directly preceding the beginning of MBRT and SME training for the second cohort of participants in Months 2 and 3.

The first phase of post-intervention data collection will occur during Year 2, Month 8, directly following the end of the scheduled MBRT and SME training for the first cohort of participants; the second phase of post-intervention data collection will occur in Year 3, Months 3-4, directly following completion of MBRT and SME training for the second cohort of participants. Qualitative data collection (i.e., individual feedback interviews) for each training cohort will occur during the same months as post-intervention data collection.

The first phase of 3-month follow-up data collection (first training cohort) will occur during Year 2 Month 10; the second phase of 3-month follow-up data collection (second training cohort) will occur during Year 3, Month 6. The first phase of 6-month follow-up data collection (first training cohort) will occur during the Year 3, Month 2; the second phase of 6-month follow-up data

collection (second training cohort) will occur during the Year 3, Month 9. The first phase of 12-month follow-up data collection (first training cohort) will occur during Year 3, Month 8; the second phase of 12-month follow-up data collection (second training cohort) will occur during the Year 4, Month 1.

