## **4. SELECTION AND ENROLLMENT OF PARTICIPANTS**

### **4.1 Inclusion Criteria**

LEOs will be recruited from PPB, APD, and MPD. We will over recruit for a target final sample across sites of 20% women and 35% racial/ethnic minorities.

Eligible participants must: 1) be 21-65 years old (age limitations for both police departments); 2) demonstrate English fluency; 3) be a sworn LEO at the rank of Sergeant or below; 4) agree to random assignment to condition; and 5) be willing to complete assessments at multiple time points and participate in intervention groups.

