*Informed Consent.* Study staff will obtain informed consent via REDCap from all participants prior to screening and baseline data collection. The consent form will include information about randomization, release of information (including data from PPB and APD databases), researchers' responsibilities regarding records collected, DHHS certificate of confidentiality, registration with clinicaltrials.gov, and permission to audio and video record sessions.

*Randomization.* Study staff not involved in data collection will randomly assign participants to condition using SPSS and REDCap, stratifying for gender, using a permuted-block randomization procedure frequently used in MT trials to ensure balance within strata and across groups. The study statistician will create an allocation table using SPSS, and upload it to REDCap, which will be used to implement the randomization procedure.

Following completion of the baseline online survey and confirmed completion of the dried blood spot sample, participants will be assigned using a 2:1.5:1 ratio (MBRT = 47; SME = 35; NIC = 22), allowing more robust evaluation of measure sensitivity and responsiveness as well as more accurate parameter estimation for the MBRT group. **Randomization will occur separately at each site to ensure equal ratios at all sites across the three arms.**

Participants will be notified of group assignment via phone call by a study team member. Participants assigned to MBRT and SME conditions will receive emailed information regarding course structure, dates/times, and class format. All participants will be provided information on assessment timeline, reminder calls they will receive, and contact information for the research team. Participants assigned to SME or NIC will be offered an opportunity to attend an MBRT course after the final 12-month follow-up collection of departmental excessive use of force data.

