12-month Followup (must occur on target date, which is 360 days from the end of the intervention period):

- Excessive Use of Force (Individual-level LEO excessive use of force (i.e., aggressive drawing and discharge of weapons, vehicle rams, illegal takedowns, administrative and citizen complaints)
  - BlueTeam^96 Database and/or other departmental data

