## **9.6 Data Analyses**

### Quantitative:

Following best practice guidelines including CONSORT feasibility guidelines and past research, we will measure sensitivity (using a relative efficiency approach) and

responsiveness to change (examining within-group change over time). Relative efficiency analyses will be used to establish that our outcome measures are sensitive to differences between our treatment arm of focus (MBRT) and our other two arms - an active control arm (SME) and a no-treatment control arm (NIC). Therefore, sensitivity analyses will focus on assessing the degree to which outcomes are sensitive to study arms and not whether change is significant. Sensitivity to differences for MBRT compared to SME and NIC will be assessed by examining the relative efficiency of each outcome variable for MBRT versus SME and NIC separately. We will calculate the relative efficiency for MBRT versus SME by conducting one-way, between-subjects Analysis of Covariance (ANCOVA) analyses with MBRT versus SME as the independent variable and each outcome variable at post-training as the dependent variable; we will include study site and gender as covariates. We will also conduct ANOVAs using the same independent and dependent variables to ensure that all inferential tests are conducted and identify any potential Type II Errors among the ANCOVAs. We will then divide the *F*-statistic for each behavioral (BlueTeam/departmental use of force; individual indicators of use of force as well as a composite score of use of force using the individual indicators), physiological (C-RP, IL-6, IL-10, TNF- $\alpha$ ), and self-report (aggression, alcohol misuse, depression, suicidal ideation, trauma symptoms, burnout, and psychological resilience) outcome by the largest *F*-statistic among these analyses, such that the larger the number, the more sensitive that outcome is to the impact of MBRT relative to the active control group.

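### Departmental use of force is analysed without on-duty time, so duty lost after baseline cannot be told from a real reduction

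*Combined protocol and SAP*

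**What the plan says.** Section 1.1, Objective 2, sets an acquisition target: "We will obtain departmental excessive use of force (i.e., BlueTeam or other departmental data) for 100% of participants at all sites". The time allowed is "1 month to assemble pre-baseline, and 1 month to assemble at 12-month follow-up". Section 6.2.4 describes the 12-month content as individual-level weapon use, vehicle rams, takedowns and complaints, and says that collection "must occur on target date, which is 360 days from the end of the intervention period".

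Section 9.6 analyses "individual indicators of use of force as well as a composite score of use of force using the individual indicators". It uses these records in two ways:

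- **Between arms:** MBRT against SME, and MBRT against NIC, at post-training. The ANCOVA adjusts for site and gender, and a parallel ANOVA has no covariates.
- **Within the MBRT arm:** the SMR, which is the post-intervention mean minus the baseline mean, divided by the SD of change. This is the only responsiveness index for use of force, because the correlations with global impression of change cover self-report outcomes alone.

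Section 4.1 requires a participant to "be a sworn LEO at the rank of Sergeant or below" and does not require full-time or active status. The version 9 entry in the revision history agrees, noting that part-time officers may be eligible. Employment status is asked at the phone screen (Section 6.2.1), and the schedule in Section 6.1 has no later duty item. The missing-data rules in Sections 9.2 and 9.3 start from withdrawal from the study. The Précis ends participant involvement at 6 months and obtains the 12-month data without participant contact.

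Section 3 gives a calendar in which "the second phase of 12-month follow-up data collection (second training cohort) will occur during the Year 4, Month 1".

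**The concern.** The number of recorded events depends on an officer's conduct and on how long the officer was at work in a role where events can occur. The plan observes the events but not the time at work. An officer who leaves the force in month 8 still has a departmental record, so the record counts as obtained, and its zeros look like good conduct. No missing-data rule applies, because the officer may never have withdrawn from the study. After month 6 nobody is in contact with the officer to find out. If duty dates are not requested with the data, the analysts have no planned source from which to repair this later.

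Section 9.1 makes it an important objective to show that this measure is useful as a research outcome, and says that its responsiveness has not been assessed. Section 1.1, Objective 4, uses sensitivity and responsiveness to choose outcomes for the future trial. A fall produced by absence would move use of force up that ranking for the wrong reason.

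**Working it through.** **No plan figure to reproduce.** The 100% is a target, and Section 9.2 says that no power analysis was made. The documents give no event rate, leave rate, resignation rate or part-time share. The sizes below are therefore illustrations on assumed inputs.

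**Inputs (assumed).** f = share of officers who lose duty time after baseline; d = fraction of the follow-up window that they lose; m = events per officer over a full 12-month window. Baseline and follow-up windows are equal, the true effect is zero, and counts are Poisson with gamma variation between officers (shape 2, so the variance of the officer effect is 0.5 and its mean square is 1.5).

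**Raw count ratio.** Follow-up mean / baseline mean = 1 - f×d.

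- f = 5%, d = 25%: 1 - 0.0125 = 0.99
- f = 20%, d = 50%: 1 - 0.10 = 0.90
- f = 20%, d = 100%: 1 - 0.20 = 0.80

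**SMR on raw counts.** Mean change = -m×f×d. Variance of change = m(2 - f×d) + m²(1.5×f×d² - f²×d²).

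For f = 20% and d = 50%, the last bracket is 1.5×0.2×0.25 - 0.01 = 0.065:

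| m | mean change | variance of change | SMR |
|---|---|---|---|
| 0.5 | -0.05 | 0.5×1.9 + 0.25×0.065 = 0.966 | -0.05 / 0.983 = -0.05 |
| 2 | -0.20 | 2×1.9 + 4×0.065 = 4.06 | -0.20 / 2.015 = -0.10 |
| 5 | -0.50 | 5×1.9 + 25×0.065 = 11.125 | -0.50 / 3.335 = -0.15 |

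Simulation with the same inputs gave -0.052, -0.100 and -0.151. Over the whole grid (f from 5% to 20%, d from 25% to 100%), the simulated SMR ran from -0.01 to -0.25. Dividing by duty time brought the rate ratio back to 1.00 (0.995 to 1.006).

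**Between arms.** Raw ratio = (1 - f₁×d) / (1 - f₂×d).

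- Equal loss (10% and 10%): 1.00
- 20% against 10%, d = 50%: 0.90 / 0.95 = 0.95
- 20% against 10%, d = 100%: 0.80 / 0.90 = 0.89

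**Stable part-time work.** An officer at half time in both windows has expected counts of m/2 and m/2. The change is 0 and the level is half. In the post-training comparison, which has no baseline covariate, this adds noise or chance imbalance.

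**Calendar, cohort 2 (Section 3).** Training is in Year 3 Months 2-3, the 6-month visit in Month 9, and the 12-month collection in Year 4 Month 1. Counting Year 4 Month 1 as Month 13, it falls 13 - 3 = 10 months after training and 13 - 9 = 4 months after the 6-month visit. Twelve months after Month 3 is Year 4 Month 3. For cohort 1, the gap between the same two follow-ups is 6 months (Year 3 Month 2 to Month 8). The cohort 2 date and day 360 in Section 6.2.4 cannot both hold.

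**Timing of the analysis.** Sections 1.1 and 6.2.4 describe collection pre-baseline and at 12 months. Section 9.6 analyses every outcome, use of force included, at post-training. Neither the baseline look-back nor the follow-up window is stated.

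**The case against.** The strongest reply is that the plan states no wrong rule. The 100% is a feasibility target for obtaining records, and having every record is desirable. The text specifies neither counts nor rates, so saying that absent officers are scored as improved is an inference. The illustrated SMR is also modest: with 47 officers in MBRT its standard error is roughly 1/√47 = 0.15, so the main case reaches about one standard error at most. No efficacy hypothesis is tested and no outcome is primary.

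All of that stands as a limit on size and consequence. It does not fill the gap: without duty data, a rate could not be computed even if one were intended.

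Four stronger readings are tempting, and the documents do not support them:

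- **Part-time officers look improved.** Only a fall in hours after baseline does that; stable part-time work gives no change.
- **The arm comparison is biased.** Randomization balances duty loss in expectation. Bias needs differential loss, for which the documents give no evidence, although chance imbalance is possible with 22 officers in NIC.
- **An early cohort 2 collection lets controls receive MBRT within the measured window.** Section 4.3 says "Participants assigned to SME or NIC will be offered an opportunity to attend an MBRT course after the final 12-month follow-up collection", so the data are already taken when the offer opens, on either date.
- **The short cohort 2 window gives a larger spurious SMR.** With a window ratio of 10/12 and simple Poisson counts, -0.167m/√(1.833m) is -0.17 at m = 2 and -0.28 at m = 5. That rests on a 12-month baseline look-back that no section states, covers cohort 2 only, and measures the calendar rather than duty time. The calendar is also loose in the other direction: from cohort 1 training in Year 2 Months 4-5 to Year 3 Month 8 is about 15 months.

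**Conclusion.** The concern holds as an omission. Use of force has no on-duty denominator, no duty status is collected after the phone screen, and no rule separates a true zero from absence. The uncontrolled MBRT-arm SMR is most exposed. If 20% of officers lose half their follow-up duty, counts fall 10% and the SMR is about -0.05 to -0.15 with no true effect. It reaches about -0.25 only if 20% lose the whole window at 5 events per officer-year. These sizes rest on assumed rates, equal 12-month windows and analysis of raw counts. A shorter window needs its own values of f, d and m.

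The consequence is a distorted ranking of one candidate outcome, not a false efficacy claim. The sponsor should act on it, because the measure's usability is itself under study. The two timing conflicts are separate matters of reconciliation and need no assumption about officers.

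**What to change.** - In the departmental data requests already planned, add for each officer the dates of active duty, leave, reassignment and separation, and full- or part-time status.
- State the baseline look-back and the follow-up window for use of force.
- Analyse events per on-duty month, or model counts with log on-duty time as an offset. Treat time after separation as unobserved, not as zero.
- Report duty time by arm beside the use-of-force results.
- Reconcile the cohort 2 date in Section 3 with day 360 in Section 6.2.4.
- Reconcile collection pre-baseline and at 12 months (Sections 1.1 and 6.2.4) with the post-training analysis in Section 9.6.

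The timing of the MBRT offer to SME and NIC needs no change on this account.

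The cost is a few extra fields in an existing request and some wording. The consent release may need to name employment-status data, and some officers will contribute less than the full window.

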#### **Objective 4: Assess participant experience and optimize outcome measures across sites.**

Well-developed content themes with data saturation emerging from feedback interviews will provide information on acceptability, impact of assessments, protocol and intervention fidelity, and equivalence of these markers across sites. Benchmark sensitivity and responsiveness values will determine the most sensitive and responsive measures relative to all study outcomes, versus a significance testing approach in which standardized/conventional threshold values are used to make decisions regarding significance. Sensitivity and responsiveness information will determine which outcomes are most impacted by MBRT for retention in a future full-scale multi-site efficacy trial. Benchmarks for equivalence across sites will be evidenced by: a) qualitative themes that suggest experiential continuity across sites, and b) equivalence in outcome measure response distributions, reliability estimates, and intraclass correlations.

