To calculate the relative efficiency of MBRT versus NIC, we will conduct one-way, between-subject ANCOVAs with MBRT vs. NIC as the independent variable, each outcome variable at post-training as the dependent variable, and gender and study site as covariates. Again, we will also conduct ANOVAs using the same independent and dependent variables to ensure all inferential tests are conducted and identify any potential Type II Errors among the ANCOVAs. We will then divide the *F*-statistic for each behavioral, physiological, and self-report outcome by the largest *F*-statistic among these analyses; again, the larger the number, the more sensitive the outcome is to MBRT relative to the no-treatment control group. These sensitivity analyses will allow assessment of which behavioral, physiological, and self-report outcomes are most sensitive to MBRT.

Responsiveness to change across time will be assessed in the MBRT arm for behavioral, physiological, and self-report outcomes by: 1) calculating and comparing standardized mean responses (SMR) for outcomes by subtracting the baseline mean response for each outcome from the post-intervention mean response for that outcome, and dividing by the standard deviation of change for that outcome; 2) calculating and comparing partial correlation coefficients (adjusting for study site and gender) between a global impression of change measure that captures the subjective experience of changes in stress, job performance, and resilience at post-intervention and residualized change scores (baseline to post-intervention) for each self-report outcome. For both SMR values and correlation coefficients, the higher the absolute value, the more responsive the outcome is to change across time in the MBRT arm. We will conduct additional correlation analyses using the same variables without adjusting for study site and gender to identify any potential Type II Errors among the partial correlations.

In addition, we will examine data for any indications of systematic site differences. Using baseline data (where sample size will be greatest) and pooling arms, since no treatment differences are expected at baseline, distributions of standardized responses on outcome measures will be summarized, graphed, and compared across sites. Key parameters, reliability

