estimates (i.e., Cronbach's alpha), and intraclass correlations will be estimated and checked for discrepancies between sites. Identified discrepancies will be investigated to determine site-specific issues that would undermine assumptions of conceptual and structural equivalence of measurement.

Given the optimization aim of our study, our analyses will not adjust for intraclass correlations across study arms (and any heterogeneity in those correlations). Our study will allow us to obtain information about the magnitude of intraclass correlations and the degree to which they are heterogeneous across study arms, which we will use for our data analysis plan in a future fully-powered efficacy RCT.

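### Objective 4's benchmark (b) would label the sites equivalent on the strength of graphs and a discrepancy check, which with 26, 26 and 52 officers cannot reliably exclude moderate site differences

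*Combined protocol and SAP*

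**What the plan says.** Objective 4 (Section 1.1) sets two benchmarks for equivalence across sites. Strand (a) is qualitative, resting on interview themes. Strand (b) is "equivalence in outcome measure response distributions, reliability estimates, and intraclass correlations".

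Section 9.6 (Quantitative) describes the analysis behind strand (b). It is done "Using baseline data (where sample size will be greatest) and pooling arms". The method for distributions is that "distributions of standardized responses on outcome measures will be summarized, graphed, and compared across sites". For the other two elements, Cronbach's alpha and "intraclass correlations will be estimated and checked for discrepancies between sites". On follow-up it says: "Identified discrepancies will be investigated to determine site-specific issues that would undermine assumptions of conceptual and structural equivalence of measurement".

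Neither section gives a confidence interval for a site difference, a size at which a difference counts as a discrepancy, or a rule for accepting equivalence. The Précis gives the planned site sizes as 52 (Albuquerque), 26 (Portland) and 26 (Madison). Section 9.2 justifies the sample size by a recommendation of 12-25 participants per arm and does not discuss precision per site.

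**The concern.** Strand (b) offers equivalence as the evidence for equivalence. The only way to meet it under Section 9.6 is for nobody to notice a discrepancy. At these site sizes that can easily happen while the sites differ by a moderate amount in mean level, spread or reliability. Objectives 1 to 3 state numeric criteria; this strand has none, so a reader of the results could not tell what size of difference had been ruled out.

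At stake is the information passed to the planned multi-site efficacy trial. An equivalence statement on measurement, once made, may be taken as a reason not to look at the question again, although the data behind it would leave it largely open.

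**Working it through.** **Inputs from the documents.** Site sizes are 52, 26 and 26, and arm sizes 47, 35 and 22 (Précis). Baseline data are used with arms pooled (Section 9.6), so the full site sizes are available at best. Up to 15% of data are expected missing from active participants (Objective 2).

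**Plan's own figures.** 52 + 26 + 26 = 104 and 47 + 35 + 22 = 104, as stated. The plan gives no precision, power or margin for the site comparison, so there is nothing further to reproduce.

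**Assumptions.** Responses are on a common SD scale (SD = 1). The yardsticks of 0.5, 0.8 and 1.0 SD are mine; the documents name no margin. The 15% missing case is pessimistic for baseline, because randomization requires the baseline survey to be completed.

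**Step 1: precision of a difference in site means.** Half-width = 1.96 × sqrt(1/n1 + 1/n2).

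| Comparison | SE (SD units) | 95% half-width |
|---|---|---|
| 26 v 26 | sqrt(1/26 + 1/26) = 0.277 | 0.54 |
| 52 v 26 | sqrt(1/52 + 1/26) = 0.240 | 0.47 |
| 22 v 22 (15% missing) | sqrt(1/22 + 1/22) = 0.302 | 0.59 |
| 44 v 22 (15% missing) | sqrt(1/44 + 1/22) = 0.261 | 0.51 |

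Using t quantiles adds about 0.01 to 0.02 SD.

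**Step 2: chance of demonstrating equivalence when the sites are truly identical.** For two one-sided tests (TOST) at 0.05 each, power = 2Φ(margin/SE − 1.645) − 1. For 26 v 26:

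- 0.5 SD: 0.5/0.277 − 1.645 = 0.158, power about 12%.
- 0.8 SD: 0.8/0.277 − 1.645 = 1.24, power about 79% (77% by t-based simulation).
- 1.0 SD: 1.0/0.277 − 1.645 = 1.96, power about 95% (94% by simulation).

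For 52 v 26 at 0.5 SD it is 33-34%. The smallest margin with 80% power is (1.645 + 1.282) × SE, that is 0.81 SD for 26 v 26 and 0.70 SD for 52 v 26.

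**Step 3: chance of missing a real difference.** If the two 26-officer sites truly differ by 0.5 SD, a two-sided 5% test has z = 0.5/0.277 − 1.96 = −0.16, so it misses the difference about 56% of the time. The plan specifies no such test; the figure shows how little a comparison of this size can reveal.

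**Step 4: reliability and spread.** By the F-based (Feldt) interval, an illustrative alpha of 0.85 on an assumed 10-item scale at n = 26 has a 95% CI of about 0.75 to 0.92. For the ratio of SDs between two 26-officer sites, the 95% factor is sqrt(F(0.975; 25, 25)) = 1.49, so spread is known only within a factor of about 1.5.

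**Not computed.** I give no figure for intraclass correlations, because Section 9.6 does not say which grouping they refer to at baseline.

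**The case against.** The strongest reply is that Section 9.6 describes a screen: look for signs of site differences and investigate any that appear. That is proportionate for a feasibility trial that disclaims power, and site is in any case a covariate in the main models. This stands as a defence of Section 9.6. It does not defend Objective 4, which gives the outcome of that screen the name of equivalence.

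Three stronger readings are tempting and are not supported.

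- *A reader might infer that the benchmark cannot be met at all, because half an SD can never be excluded.* The documents set no 0.5 SD margin, and at 0.8 to 1.0 SD the small sites have fair to good power. Even at 0.5 SD, the strict statement holds only for Portland v Madison with a 95% interval. The 90% interval used in TOST has a half-width of 0.46 SD there, and the 95% half-width for 52 v 26 is 0.47 SD, so an observed difference near zero would exclude 0.5 SD in either case.
- *A reader might infer that the trial's central equivalence aim fails.* The Précis and Objective 2 speak of equivalence of procedures, and Objectives 2 and 3 attach their own numeric criteria for training, errors, acceptability and fidelity. Strand (b) is one part of one objective, beside the qualitative strand.
- *A reader might infer that the plan commits to reporting equivalence whenever no discrepancy is seen.* No sentence says so. The problem is that the benchmark's wording permits it and nothing in the analysis section prevents it.

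It is also fair that officers in three different departments may differ in mean level while the instruments work equally well, so equal means are not required for equivalence of measurement. But strand (b) itself names response distributions, and the alpha interval shows that reliability is imprecise too.

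**Conclusion.** The concern holds in limited form. Objective 4(b) promises a label that the analysis in Section 9.6 cannot support. At the planned site sizes, a finding of no discrepancy is compatible with mean differences of roughly half an SD and with noticeably different reliability. The half-widths rest only on the planned site sizes and a common SD. The 12%, 77-79% and 94-95% figures depend on assumed margins and on truly identical sites; the alpha interval depends on an assumed 10 items and an illustrative value of 0.85. The plan needs correcting because following it as written would allow an unsound conclusion, but neither the design nor the sample size is at fault.

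**What to change.** In Objective 4(b) and the matching text of Section 9.6, replace the equivalence wording with a descriptive check for large site differences. For each outcome measure, report between-site differences in means and SDs, Cronbach's alpha and intraclass correlations with 95% confidence intervals, and state in words the largest difference the data do not exclude. Say which intraclass correlation is meant. This fits Section 9.1, which already makes the estimation of confidence intervals an analytic aim.

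No margin, significance test or added enrolment is needed. The cost is a few sentences, some extra table columns and a weaker claim. Strand (a) and the procedural criteria in Objectives 2 and 3 stay as they are.
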